#### **7.4 Interim Analyses and Data Monitoring**

No interim analyses are planned for this study.

#### **7.5 Multi-center Studies**

No multi-center analyses are planned for this study.

### **8 Summary of Study Data**

All continuous variables will be summarized using the following descriptive statistics: n (non-missing sample size), mean, standard deviation, median, maximum and minimum. The frequency and percentages (based on the non-missing sample size) of observed levels will be reported for all categorical measures. In

general, all data will be listed, sorted by site, subject, and when appropriate by visit number within subject.

All summary tables, unless otherwise stated, will be structured with one column for the trial vaccine (HIL-214) and will be annotated with the total population size relevant to that table, including any missing observations.

### **8.1 Subject Disposition**

Completion/withdrawal from the study, together with reasons for withdrawal from the study for subjects in the safety analysis set will be listed and the following will also be tabulated:

- Number and percentage of subjects who completed the study.
- Number and percentage of subjects withdrawn from the study and the principal reason for withdrawal.

For subjects in the enrolled set who fail to meet the eligibility criteria the reasons for failure, including the inclusion/exclusion criteria that were not met will be summarized and listed.

The number and percentage of subjects in the enrolled set with data available for each scheduled visit will be summarized and listed.

The number and percentage of subjects included in each analysis set and the reasons for exclusion will be summarized and listed.

### **8.2 Protocol Deviations**

The number and percentage of subjects in the safety analysis set with at least one important protocol deviation will be summarized by deviation category (major/minor).

The final PD data will be reviewed during the data review meeting and updated by the statistics group to add the important protocol deviations flag and the deviation categories.

All protocol deviations will be listed.

### **8.3 Demographic and Baseline Variables**

Demographic and baseline variables will be summarized descriptively. The variables that will be summarized are:

- Age (years)
- Age (years) by category:
  - 18 to 65 years
- Sex:
  - Male
  - Female
  - Other/Not Recorded
- Race:

- American Indian or Alaskan Native
  - Asian
  - Black or African American
  - Native Hawaiian or Other Pacific Islander
  - White
  - Other
  - Not Reported
  - Unknown
- Ethnicity:
  - Hispanic or Latino
  - Not Hispanic or Latino
  - Not Reported
  - Unknown
- Weight (kg)
- Height (cm)
- BMI (kg/m^2)

#### 8.4 Concurrent Illnesses and Medical Conditions

Medical history will be coded using the latest available version of the Medical Dictionary for Regulatory Activities (MedDRA®). The dictionary version used will be 25.1.

Concurrent illnesses and medical conditions will be classified as 'current' if the end date is on or after Visit 1 (Day 1), or the condition has been marked as ongoing. Illnesses and medical conditions that start and end before Visit 1 (Day 1) will be classified as past.

Past and current medical history will be summarized and listed for the safety analysis set. All medical history summaries will be ordered by the MedDRA internationally agreed order (**Appendix 1**) for system organ class (SOC), and decreasing frequency of preferred term (PT) within SOC. A subject who has multiple events in the same SOC and PT will be counted only once in the subject counts but all events will be included.

#### 8.5 Prior and Concomitant Medications and Other Vaccinations

**Prior medication definition:** If a subject takes a medication before Visit 1 (Day 1), this medication will be classified as 'prior medication'. With this definition, any medication recorded that has been taken for at least 1 day and has been stopped before Visit 1 (Day 1) will be considered as prior.

**Concomitant medication definition:** Prior medication not stopped before Visit 1 (Day 1) will be classified as 'concomitant medication'. Medication will be labelled as 'concomitant medication' when the start date is between Day 1 and the final study visit (Day 85) or, in case of early termination, on the date of the subject's last visit. With this definition, any medication that has been taken for at least 1 day between Visit 1 (Day 1) and Day 85 will be considered as concomitant.

Other vaccinations will be determined as prior or concomitant using the same definitions as medications.

Medications and other vaccinations will be coded according to the 2020 version of the World Health Organization Drug Dictionary (WHODD). Medical procedures will not be coded.

Prior and concomitant medications and other vaccinations will be summarized and listed for the safety analysis set.

## **9 Immunogenicity Analysis**

The primary endpoint will consider the immunogenicity of HIL-214 at Visit 3 (Day 29) and all analysis will be defined in this section. Analyses will be completed for the safety analysis set and per protocol analysis set. Subjects with immunogenicity samples taken outside of the visit windows (as described in **Table 1**) will not be included in analyses which use the per protocol analysis set.

The immunogenicity variables, HBGA-blocking titers and total immunoglobulin (pan-Ig) titers that are specific for GI.1 VLP and GII.4c VLP will be summarized. Along with the following summaries, the immunogenicity data will be listed by subject.

### **9.1 Main Analytical Approach**

For all immunogenicity variables a standard summary of the number of subjects with an assessment (n), mean, standard deviation, median, Q1, Q3, minimum and maximum will be presented alongside the number of assessments below the LLOQ and LLOD and above the ULOQ. The number of subjects that are missing an assessment will also be summarized.

As well as the standard continuous summary of the outcomes, geometric mean titers (GMTs), geometric mean fold rise (GMFR) and seroresponse rate (SRR) will be presented (as defined in **Sections 5.3.2 and 5.4**) for each immunogenicity variable. The 95% confidence intervals (CI) for GM, GMFR and SRR as well as geometric standard deviation (GSD) will also be provided.

In addition, for each immunogenicity variable a reverse cumulative distribution curve will be produced, with titer on the x-axis and the percentage of subjects below the titer value on the y-axis.

Line graphs and boxplots summarizing the GMT for each trial vaccine group for the serotypes GI.1 and GII.4 will also be produced. These outputs will both have the visits of baseline (Day 1) and Visit 3 (Day 29) on the x-axis and the GMT on the y-axis, presenting data on the log scale.

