## 6 Sample Size

A sample size of 80 subjects will provide sufficient serum for the establishment of proficiency panels to confirm assay validation of the validated serology assays planned to support the clinical development plan for HIL-214.

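### Does the axis wording for the reverse cumulative distribution curve in SAP 9.1 need to be corrected?

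*SAP*

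**What the plan says.** SAP 9.1 first sets out the tabulated results for each immunogenicity variable: standard summary statistics, GMT, GMFR, SRR, GSD and 95% confidence intervals. It then adds a figure for every one of them: "reverse cumulative distribution curve will be produced, with titer on the x-axis and the percentage of subjects below the titer value". The closing phrase of that quote defines the vertical axis.

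The variables are listed at the start of SAP Section 9: "The immunogenicity variables, HBGA-blocking titers and total immunoglobulin (pan-Ig) titers that are specific for GI.1 VLP and GII.4c VLP will be summarized". That is two assays for each of two antigens, so four variables.

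Nothing else in the documents defines the curve. SAP 5.3.2 and 5.4 define fold increase, seroresponse, the handling of values outside the assay limits, geometric means and GMFR. Protocol 13.1.3 asks for GMT, GMFR, SRR and their intervals and does not mention this figure. The amendment table in SAP Section 15 records, for Section 9.1, only the added line graphs and boxplots.

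**The concern.** The sentence gives two instructions that cannot both be followed. By its name, the curve should descend: at each titer it gives the share of subjects who reach that titer or more. By its axis text, the curve should ascend: at each titer it gives the share who fall short.

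Direction matters when such figures are read. On a reverse curve, a population with higher titers lies higher and further to the right. On an ordinary cumulative curve, the same population lies lower. A reader who trusted the title and ignored the axis could take a stronger response for a weaker one. The figure is planned for all four primary immunogenicity variables, so the slip is repeated across them.

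**Working it through.** The plan states no figure for this point, so there is none to reproduce. The check is of the two definitions.

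**Inputs**
- Plot name and axis text: SAP 9.1, as quoted.
- Number of variables: 2 assays × 2 antigens = 4 (SAP Section 9).
- Planned number of subjects: 80 (SAP Section 6), used only for illustration.
- Titer distributions: log-normal, geometric mean 100 or 800, GSD 3. These are assumptions made for illustration; the documents give no titers.

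**Step 1: definitions.** With *n* subjects and titers *T*:
- axis text: B(x) = 100 × (number with T < x) / n
- name: A(x) = 100 × (number with T ≥ x) / n

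Every subject is counted in exactly one of the two, so A(x) + B(x) = 100 at every x. One curve is the other with y replaced by 100 − y.

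**Step 2: ties.** SAP 5.3.2.3 gives all values below the LLOD one common number, so ties are likely. The identity still holds. Suppose 24 of 80 subjects (24/80 = 30%) share the lowest value. At that value B = 0% and A = 100%, and the sum is 100. Ties do mean that no fixed gap between the curves can be assigned to a quartile. In this example the first quartile equals the minimum, and 0% rather than 25% of subjects lie below it.

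**Step 3: illustration.** With F(x) = Φ(ln(x/GMT)/ln 3), where Φ is the standard normal distribution function:

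| Assumed GMT | Titer x | Below x (axis text) | At or above x (name) |
|---|---|---|---|
| 100 | 25 | 10.3% | 89.7% |
| 100 | 100 | 50.0% | 50.0% |
| 100 | 400 | 89.7% | 10.3% |
| 800 | 100 | 2.9% | 97.1% |

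At titer 100, the population with GMT 800 plots above the one with GMT 100 on the reverse curve (97.1% against 50.0%) and below it on the ordinary curve (2.9% against 50.0%). In a simulated sample of 80 with GMT 100, 7.5% were below titer 25 and 92.5% at or above it. The sum was 100 at every titer checked.

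**Step 4: what depends on the choice.** GMT and GSD come from the log titers, GMFR from the log fold increases, and SRR from the count with at least a 4-fold rise. None uses the curve. The line graphs and boxplots in SAP 9.1 are specified separately. Number of estimates or intervals changed: 0.

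**Step 5: can a wrong drawing go unnoticed?** At the lowest observed titer, which SAP 9.1 already reports as the minimum, the curve must read 100% if it is the reverse curve and 0% if it is the ordinary one, whatever the ties. The shape alone shows which was drawn.

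**The case for a change.** The best case for a correction is that the axis text is the more specific instruction. A programmer who followed it would be complying with the SAP, and the result would contradict its own title. If the figure were programmed twice independently, the two versions might not match. Putting it right takes one phrase and touches no data. A plan should not be right only when half of a sentence is ignored.

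The factual part stands in full: the sentence is inconsistent and no other section resolves it. PDF conversion or redaction does not explain it either.

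The consequence is what does not stand. The word *reverse* has no function if the percentage below is plotted, so the name shows which display was meant. If the axis text were followed and the axis labelled accordingly, curve and axis would agree and only the title would be wrong; a reader who looks at the axis is not misled. A mismatch between two programmers would bring the question up before release. The figure is an addition that the protocol does not ask for, in a single-arm trial with no comparison or decision rule resting on it, and the subject-level titers are listed.

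**Conclusion.** The inconsistency is real but clerical, and no change to the plan follows. It affects the name or axis of one supplementary figure for each of four variables. The number of figures is not fixed, because SAP 9.1 does not say which visits are drawn or whether they share a panel. No GMT, GMFR, SRR, GSD, confidence interval or conclusion changes, and the two possible curves hold the same information because they add to 100 at every titer.

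This rests on two assumptions: that whoever draws the figure labels the y-axis with the quantity plotted, and that the figure stays descriptive. Drawing the descending curve that the SAP names, with the axis labelled as the percentage at or above each titer, is the sensible reading and needs no amendment.

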## **10 Safety Analyses**

All safety analysis is defined in this section and will be completed for the safety analysis set. Along with the following summaries, all safety endpoints will be listed by subject.

All safety summaries of continuous variables will present n (non-missing sample size), mean, standard deviation, median, maximum and minimum.

### **10.1 Adverse Events**

All unsolicited AE summaries will be ordered by the MedDRA internationally agreed order (**Appendix 1**) for system organ class (SOC), and decreasing frequency of preferred term (PT) within SOC. A subject who has

multiple events in the same SOC and PT will be counted only once in the subject counts but all events will be included.

#### **10.1.1 Severity of Adverse Event**

In summaries including severity, the following intensity categories will be summarized: 'Mild', 'Moderate', 'Severe'. For the solicited AEs of redness, swelling, and induration the following categories of severity will be summarized: '<25mm', '≤25-50mm', '>50-100mm', '>100mm'. For fever the following categories of severity will be summarized: '<38°C', '≥38-39°C', '≥39-40°C', '≥40°C'. Subjects who experience the same event multiple times will be included in the most severe category. Missing severities are not expected, however if these occur they will not be imputed but will be included in relevant summary tables under a missing category.

#### **10.1.2 Relationship to Trial Vaccine and Procedures**

In summaries including relationship to trial vaccine and relationship to trial procedures, the following relationships will be summarized: 'Not Related', 'Related'. Subjects who experience the same event multiple times will be included in the most related category. Missing relationships are not expected, however if these occur they will not be imputed but will be included in relevant summary tables under a missing category.

#### **10.1.3 Solicited Adverse Events**

The solicited safety parameters for this study are the local adverse events (injection site reactions) of pain, erythema (redness), induration and swelling and the systemic adverse events of headache, fatigue, myalgia, arthralgia, vomiting, diarrhea and fever (defined as body temperature greater than or equal to 38°C regardless of methods used).

Solicited reactions will be assessed 30 minutes after administration of the trial vaccine, and then daily for 7 days (including the day of administration).

Body temperature measurements will be summarized in categories (including fever), without adjustment for the route of measurement. Summaries of the day of first onset of each event and the maximum number of continuous days subjects experienced each event will also be provided.

Any solicited local or systemic reactions observed as continuing beyond 7 days following the trial vaccine dose will be recorded as an unsolicited AE in the case report form (CRF).

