13.1.4 Secondary Analysis - Safety

Safety data will be summarized by computing number and percentage of subjects who experienced an AE.

Solicited AEs

Solicited AEs will be assessed 30 minutes after administration of trial vaccine then daily for 7 days (including the day of administration). Summaries will be provided for each solicited AE, daily from Day 1 to Day 7 after administration of trial vaccine (including the day of dose) and overall. Solicited local AEs and systemic AEs will also be summarized by severity. For subjects

CONFIDENTIAL

with more than 1 episode of the same event within the Day 1 to Day 7 period, the maximum severity will be used for overall tabulations. Body temperature measurements will be summarized in categories (including fever, defined as temperature $\geq 38^{\circ}\text{C}$). Summaries of the day of first onset of each event and the number of days subjects experienced each event will also be provided. Data from the 30-minutes assessment will be summarized separately.

Unsolicited AEs

Unsolicited AEs, SAEs, and AEs leading to withdrawal from the trial will be coded using the MedDRA and summarized by preferred term (PT) and system organ class (SOC). Subjects reporting more than 1 occurrence for the term (level) being summarized will be counted only once for this term. Unsolicited AEs collected up to 28 days after administration (including the day of administration) of trial vaccine, will be summarized by severity (mild, moderate, severe) and relationship (not related, related) to trial vaccine or trial procedures. If a subject reported more than one AE within an SOC or PT then the event with the maximum severity and strongest relationship (causality) to trial vaccine or trial procedure will be included in the summaries. Any unsolicited AE will be summarized using the day of onset for the following 3 time intervals: 1) Day 1 to Day 28, 2) Day 1 to Day 7, and 3) Day 8 to Day 28.

SAEs and AEs leading to withdrawal from the trial will be summarized for Day 1 to Day 28, and overall (up to Day 85).

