##### **10.1.3.1 Summaries**

The summaries for solicited AEs will be:

- The number and percentage of subjects with solicited local and systemic reactions during the first 7 days (including day of administration) after the trial vaccine dose by day and overall.
- The number and percentage of subjects with solicited local and systemic reactions during the first 7 days (including day of administration) after the trial vaccine dose by severity, day and overall.
- The number and percentage of subjects with solicited local and systemic reactions during the first 30 minutes after the trial vaccine dose.

- The number and percentage of subjects with solicited local and systemic reactions during the first 30 minutes after the trial vaccine dose by severity.
- Summary of the day of first onset of each solicited AE.
- Summary of the duration (days) of each solicited AE.

A horizontal stacked bar plot showing the percentage of participants with each solicited AE after the trial vaccine dose. This plot will break down the percentages by maximum severity, with the percentage of mild, moderate and severe events stacked for each solicited AE.

All solicited AEs will also be listed.

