## **13 Summary of Changes to the Protocol**

The SAP is based on the latest Protocol which is version 3.0 dated 25th October 2023.

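### The SAP replaces the protocol's count of days with each solicited event by the longest unbroken run of days, without declaring the change

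*SAP*

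**What the plan says.** Protocol 13.1.4, on solicited events, says: "Summaries of the day of first onset of each event and the number of days subjects experienced each event will also be provided". The trial summary in Protocol 2.0 says the same. Nothing there requires the days to be consecutive.

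SAP 10.1.3 carries the same sentence with a different measure: "Summaries of the day of first onset of each event and the maximum number of continuous days subjects experienced each event will also be provided".

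The list of outputs in SAP 10.1.3.1 then has the entry "Summary of the duration (days) of each solicited AE". It gives no definition, so the only wording in the SAP that says what is counted is the sentence in 10.1.3.

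SAP section 13, the place for departures from the protocol, consists of one statement: "The SAP is based on the latest Protocol which is version 3.0 dated 25 th October 2023". The amendment table (SAP 15.1, Table 3) records a figure added to 10.1.3.1 and severity categories added to 10.1.1. It has no entry on duration.

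**The concern.** A total count of event days and a longest run are different variables. They part company when a subject has the event, is free of it for at least one day, and has it again. Protocol 13.1.4 foresees more than one episode of the same event in the seven-day window, because it gives a severity rule for that case: "the maximum severity will be used for overall tabulations". SAP 10.1.1 likewise has a rule for subjects with the same event several times.

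Safety is the trial's only secondary objective, and solicited local and systemic events are two of its five secondary endpoints. If the SAP is programmed as written, a summary that the protocol specified will not be produced. The one that takes its place can only equal it or fall below it. A reader of a table headed simply as duration in days could not tell which measure was used.

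**Working it through.** The plan states no figure for duration, so there is none to reproduce. The check compares the two definitions over every diary pattern that could occur.

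**Inputs**
- Window: seven daily records, Day 1 to Day 7 (Protocol 13.1.4; SAP 10.1.3).
- Protocol measure: days with the event (Protocol 2.0 and 13.1.4).
- SAP measure: longest unbroken run of days with the event (SAP 10.1.3).

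**Definitions.** Let x_d = 1 if the subject reports the event on Day d and 0 if not, for d = 1 to 7.
- Protocol: T = x_1 + x_2 + … + x_7.
- SAP: L = length of the longest stretch of consecutive days with x_d = 1.

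The days in the longest run are a subset of all event days, so L ≤ T always. L = T only if all event days form a single run.

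**Examples**

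| Event days | T (protocol) | Runs | L (SAP) | T − L |
|---|---|---|---|---|
| 1, 2, 3, 4 | 4 | 4 | 4 | 0 |
| 1, 2, 5, 6 | 4 | 2, 2 | 2 | 2 |
| 1, 3, 5, 7 | 4 | 1, 1, 1, 1 | 1 | 3 |
| 1, 2, 3, 5, 6, 7 | 6 | 3, 3 | 3 | 3 |

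**All patterns**
- Patterns with at least one event day: 2^7 − 1 = 127.
- Single-run patterns: 7 + 6 + 5 + 4 + 3 + 2 + 1 = 28. In all of these T − L = 0.
- Patterns with two or more runs: 127 − 28 = 99. In all of these L < T: by 1 day in 55, by 2 days in 39 and by 3 days in 5 (55 + 39 + 5 = 99).

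These are counts of possible patterns, not expected frequencies. They establish the direction of the difference and its range per subject and event. They do not say how often it will occur.

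**The case against.** **The SAP is entitled to define variables.** Protocol 13.1 leaves further detail on analysis variables to the SAP, so a reader could take the longest run as such a detail. That would hold if the protocol had said only duration. It names the quantity, a count of days, and the SAP names another. This goes beyond added detail and should at least be declared.

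**The information is reported elsewhere.** This largely stands. SAP 10.1.3.1 tabulates each reaction by day and overall, and lists every event. The Day 1 to Day 7 counts, added up and divided by the overall count, give the mean event days per affected subject, provided those counts leave out the 30-minute data that are reported separately. The median and spread of the protocol's measure can be rebuilt only from the listings. The loss is therefore a specified summary, not the data.

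**Stronger readings that the documents do not support**
- A reader might infer that the two secondary endpoints are biased downward. They are not: incidence, daily incidence, maximum severity and first onset do not use this measure. The longest run is a legitimate descriptive quantity that misleads only when read as total event days.
- A reader might attach a percentage by placing event days at random in the week. With 3 event days the mean longest run would be 65/35 = 1.86, about 38% below 3. Nothing in the documents supports random placement, so this is not an estimate for the trial.
- A reader might argue that symptoms such as headache or fatigue often recur after a gap. The documents say only that repeat episodes are possible.
- A reader might add that blank diary days, which Protocol 9.3.3 leaves missing, break a run and shorten it further. Neither document says how a blank day is treated within a run, and a blank day is also absent from the protocol's count.

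**Conclusion.** The point holds as an undeclared mismatch between protocol and SAP in one descriptive safety summary. For an event in one unbroken run it makes no difference. For a subject whose episodes are separated by at least one event-free diary day, the SAP figure is lower by 1 to 3 days and is never higher. This rests only on the two definitions and the seven-day window. It also takes the duration listed in SAP 10.1.3.1 to mean the run described in 10.1.3, the only measure that the SAP describes.

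The average effect on the table cannot be computed, because the documents give no rate of intermittent events. No test depends on this summary, and the sample size is justified by serum supply alone. The point is modest, but it is worth settling before the tables are programmed.

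**What to change.** In SAP 10.1.3 and 10.1.3.1, define the duration summary as the number of diary days from Day 1 to Day 7 on which the subject reported the event, in line with Protocol 13.1.4. If the longest continuous run is also wanted, report it as a separate row, label it as such, and declare it in SAP section 13 as an addition to the protocol.

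Keeping only the longest run, with a clear label and a declared and justified change in section 13, would also remove the contradiction. It would still drop a summary that the protocol specifies, so reporting both is the better course.

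The cost is one SAP sentence and one programming derivation. No new data are needed.
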